### **6.3.3 Safety Analysis**

The frequencies of AEs by type, body system, severity and relationship to study intervention will be summarized. SAEs (if any) will be described in detail.

AE incidence will be summarized along with the corresponding exact binomial 95% two-sided confidence intervals.

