### 2.2 Secondary Objectives (or Aim)

The secondary objectives are to:

- Determine if there is a relationship between  $\Delta P$  strategy (25 or 15 cmH2O) with lung aeration determined by post-randomization EIT.
- Determine the relationship between  $\Delta P$  strategy (25 or 15 cmH2O) with VFDs at 28 days.
- Determine the relationship between  $\Delta P$  strategy (25 or 15 cmH2O) with mortality at 28 days, PICU discharge, and hospital discharge.
- Determine the relationship between  $\Delta P$  strategy (25 or 15 cmH2O) with new oxygen- or ventilator-dependency at discharge.
- Determine the relationship between  $\Delta P$  strategy (25 or 15 cmH2O) with new ventilator-associated pneumonia.
- Determine the relationship between  $\Delta P$  strategy (25 or 15 cmH2O) with new multiple organ dysfunction syndrome.
- Evaluate the tolerability and safety of the high  $\Delta P$  (25 cmH2O) strategy in pediatric ARDS.

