## 3.2 Allocation to Treatment Groups and Blinding

**Randomization and Monitoring:** Randomization will be performed in 1:1 permuted blocks using a randomization module available in Research Electronic Data Capture (REDCap). Treatment allocation will be concealed to the clinical team until after enrollment has been confirmed. Compliance with assigned treatment group, adherence to ventilator protocol, and adherence to protocolized co-interventions will be monitored.

**Blinding:** The intervention will not be blinded to clinicians or investigators. Blinding is not feasible for an intervention as fundamental and as clinically labile as ventilator management. To minimize selection bias that could occur due to pre-enrollment awareness of  $\Delta P$  assignment, randomization will occur only after informed consent has been obtained.

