### 3.3.2 Total Number of Study Sites/Total Number of Subjects Projected

The study will be conducted entirely at CHOP, with screening in the PICU and follow-up until hospital discharge or within 90 days of randomization.

We will enroll (consent) 180 subjects to produce an anticipated 160 evaluable subjects.

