For Aim 2, pre- and post-randomization EIT images (in the immediate 8 hours after randomization) will be used to determine the change in aeration. Lung images will be divided into 4 ROIs along the axial and sagittal planes, and impedance (i.e., aeration) will be determined for each region. Post-randomization end-expiratory lung impedance (EELZ) values and elastance (measured at the ventilator) will be compared to pre-randomization to determine whether ventilator changes results in recruitment (increased EELZ; unchanged or improved elastance), overdistension (increased EELZ; worsened elastance), or atelectasis (decreased EELZ; worsened or unchanged elastance). This analysis will be repeated with the second set of post-randomization EIT measurements (performed 24 to 72 hours after randomization), again compared to pre-randomization EIT. We will compare the proportion of subjects with improved recruitment and with overdistension, relative to pre-randomization EIT, between high and low  $\Delta P$  arms, with effect sizes presented as relative risk (RR). RR > 1 implies a greater proportion of subjects with the reported aeration (e.g., recruitment) with high  $\Delta P$ .

We will compute the posterior probability under minimally informative priors for any benefit when comparing 28-day mortality, PICU mortality, and hospital mortality between high and low  $\Delta P$  arms. Effect sizes will be presented as RR, with RR < 1 meaning lower mortality risk with high  $\Delta P$ . Additional analyses will be conducted with standardized priors reflecting pessimistic (priors centered at RR 1.2) and optimistic (priors centered at RR 0.8) scenarios, and with data-driven priors using effect sizes from prior adult  $V_T$  trials, including ARMA.

Analyses of VFDs and other free-day clinical endpoints will be conducted as described above for hypoxemia resolution, with death prior to the main event being treated as a competing risk and effect sizes presented on the HR scale with HR > 1 meaning superiority of high  $\Delta P$  ventilation. The main analyses will be conducted using minimally informative priors (as per main analysis), with additional analyses conducted using standardized priors reflecting pessimistic (priors centered at HR 0.8) and optimistic (priors centered at HR 1.2) scenarios, and with data-driven priors using effect sizes from prior adult  $V_T$  trials.

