## **6.4 Sample Size and Power**

Sample size was evaluated using trial simulations. We assumed that time to hypoxemia resolution and competing event followed Weibull distributions, using data from > 1000 pediatric ARDS cases at CHOP between 2011 and 2023 to estimate the shape and scale parameters. Using a projected “true” HR of 1.5 favoring high  $\Delta P$  ventilation, 160 subjects would provide 80% power to detect a  $> 90\%$  probability of any benefit (HR  $> 1$ ) with high  $\Delta P$  at a type I error rate = 0.07 (10,000 simulations) assuming a minimally informative prior (centered at HR = 1 and precision = 10 [log scale]). In this phase 2A trial, we accept 80% power to detect a 90% probability of any benefit at a type I error rate  $< 0.1$  in anticipation of a larger trial.

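### Section 6.3.3 gives one-sample intervals for adverse events and no between-arm contrast, although several safety outcomes are comparative objectives

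*Protocol*

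**What the plan says.** Section 6.3.3 is short. Its first sentence is "The frequencies of AEs by type, body system, severity and relationship to study intervention will be summarized", with serious events to be described in detail. It then adds "AE incidence will be summarized along with the corresponding exact binomial 95% two-sided confidence intervals". Nothing else in the protocol states how the safety outcomes other than death are to be analysed.

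The objectives are wider than that. Section 2.2 asks for the relationship of ΔP strategy with new VAP and with new MODS, and also to "Evaluate the tolerability and safety of the high" ΔP strategy. Section 6.2 lists the section 5 safety endpoints as secondary endpoints. Section 9.4.2 names pneumothorax, other air leak and MODS as plausibly more frequent with high ΔP, and acidosis needing vasopressors and VAP as plausibly more frequent with low ΔP. The table in section 8.6 marks seven pre-specified safety outcomes: death, pneumothorax with chest tube, other air leak, VAP, MODS, vasopressor increase for acidosis, and protocol termination for failure.

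Other binary outcomes do get a contrast. Section 6.3.2 says "We will compute the posterior probability under minimally informative priors for any benefit when comparing 28-day mortality, PICU mortality, and hospital mortality" between the arms, as a relative risk, and compares EIT recruitment and overdistension in the same form. For the primary outcome, section 6.4 states that "we accept 80% power to detect a 90% probability of any benefit".

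**The concern.** An exact binomial interval describes one proportion. It does not express how two arms differ, so 6.3.3 followed literally leaves the VAP and MODS objectives, and most of the safety objective, without an answer. The trial is meant to inform a larger one, where faster oxygenation has to be weighed against pressure-related harm. Benefit arrives as a single probability with a lenient 0.90 criterion. Pneumothorax and air leak arrive as separate rates that the reader must compare by eye.

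**Working it through.** **Inputs.** Section 3.3.2: "We will enroll (consent) 180 subjects to produce an anticipated 160 evaluable subjects". Section 3.2: "Randomization will be performed in 1:1 permuted blocks". Hence 160/2 = 80 per arm. Section 6.4: true "HR of 1.5 favoring high" ΔP, 80% power, posterior P(HR>1) > 0.90, type I error 0.07, prior precision 10 on the log scale. The protocol gives no base rate for any safety outcome, so 2% to 20% in the low arm is assumed.

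**The plan's own figure.** With d events, information is I = d/4. Success requires z > 1.2816 × √((I+10)/I). The protocol does not state d. At an assumed d = 130, I = 32.5 and the cut-off is 1.2816 × √(42.5/32.5) = 1.466. Type I error is 1 − Φ(1.466) = 0.071. Power is Φ(√32.5 × ln 1.5 − 1.466) = Φ(0.846) = 0.80. The stated design is reproduced at that event count; d = 120 gives power 0.77 and d = 136 gives 0.82.

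**Interval separation in single tables.** The exact limits for x of 80 are the 2.5% point of Beta(x, 81−x) and the 97.5% point of Beta(x+1, 80−x).
- 4/80: 1.4% to 12.3%
- 10/80: 6.2% to 21.8%
- 12/80: 8.0% to 24.7%
- 17/80: 12.9% to 31.8%

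With 4/80 in the low arm, the high arm needs 17/80 before the intervals part. Two-sided Fisher p < 0.05 needs 13/80. P(RR>1) > 0.90 under flat beta priors needs 9/80 (P = 0.92; 8/80 gives 0.88). At 12/80 versus 4/80 the intervals overlap while P(RR>1) is 0.98.

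**Chance of a flag over repeated trials.** These come from exact enumeration over two Binomial(80, p) arms. Non-overlap means that the high-arm lower limit exceeds the low-arm upper limit.

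| Low → high rate | Non-overlap | Fisher p < 0.05 | P(RR>1) > 0.90, flat / Jeffreys beta |
|---|---|---|---|
| 5% → 10% | 3% | 14% | 45% / 49% |
| 10% → 20% | 11% | 35% | 69% / 71% |
| 20% → 40% | 43% | 75% | 93% / 94% |
| 5% → 15% | 19% | 48% | 80% / 83% |
| 10% → 30% | 60% | 87% | 98% / 98% |

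With equal rates between 2% and 20%, P(RR>1) > 0.90 occurs in 5% to 10% of trials with flat priors and 10% to 12% with Jeffreys priors. Non-overlap occurs in about 0.1% or fewer.

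**Effect of the prior.** Precision 10 means SD = 1/√10 = 0.316, so a 95% prior range of exp(±1.96 × 0.316) = 0.54 to 1.86. Placed on log RR, with the full binomial likelihood and a flat prior on the low-arm risk, 12/80 versus 4/80 gives P(RR>1) = 0.85. The 0.90 mark is then passed in about 5% of trials at 5% → 10% and 34% at 5% → 15%. A normal approximation gives 0.4% and 10%.

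**The case against.** - **Harm is not left wholly uncompared.** A reader might infer from 6.3.3 that no harm is contrasted between arms. Section 6.3.2 contradicts that for death and for EIT overdistension. This stands and limits the point to the other six outcomes.
- **Non-overlap is not the protocol's rule.** Section 6.3.3 describes a summary and sets no flagging criterion. This also stands: the non-overlap percentages show how insensitive separate intervals are, not how the trial will decide.
- **A tripling is not always missed.** A reader might infer that even a tripling would usually go unseen. On the non-overlap reading that holds only below a base rate of about 9%, and no base rate is given.
- **Safety oversight exists.** The DSMB reviews events at least every six months and the Medical Monitor assesses all serious events. That protects participants, but sections 4.4 and 6.5 attach no numerical contrast to it, and it does not supply the final comparison.
- **Sample size is the main limit.** At two-sided 0.05, 80% power needs 435 per arm for 5% versus 10% and 141 for 5% versus 15%. True, but an estimated contrast with its uncertainty is still more informative than two separate intervals.
- **The statistical analysis plan may add this.** It is not at hand. Silence about arm also does not show that tables will be pooled. The point rests on the method that 6.3.3 does fix, which does not match the objectives in section 2.2.

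**Conclusion.** The point holds in this limited form. For pneumothorax, other air leak, VAP, MODS, acidosis needing vasopressors and protocol termination, the only stated method is a frequency summary with one-sample intervals, while the protocol asks comparative questions about several of them and predicts arm differences in all but the last. If separate intervals were read for non-overlap, a doubling would be missed in more than half of trials at every base rate from 2% to 20%. The result for a tripling depends on the base rate. The gain from a contrast depends on its prior: large with weak beta priors, and at low event rates small or absent if precision 10 is placed on log RR. Section 6.3.2 does not restate the precision for relative risks, but 10 is the only value the protocol gives.

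**What to change.** In section 6.3.3, state that each pre-specified safety outcome in the section 8.6 table is reported by randomised arm, with counts, the between-arm relative risk or risk difference, its 95% credible interval and P(RR>1). Present these beside P(HR>1) for the primary outcome, and keep the exact intervals as description. Name a weak prior for these contrasts, such as a flat or Jeffreys beta on each arm's risk, rather than letting precision 10 on log RR carry over.

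The cost is a paragraph of wording and a few model fits, with no new data. If 0.90 is used as a mark, expect a false alarm in roughly 5% to 12% of cases per outcome under no effect. Over six outcomes, at 10% each and if independent, the chance of at least one is 1 − 0.90^6 = 0.47. The probabilities should therefore be read together with the intervals and not as six separate tests.

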## **6.4 Sample Size and Power**

Sample size was evaluated using trial simulations. We assumed that time to hypoxemia resolution and competing event followed Weibull distributions, using data from > 1000 pediatric ARDS cases at CHOP between 2011 and 2023 to estimate the shape and scale parameters. Using a projected “true” HR of 1.5 favoring high  $\Delta P$  ventilation, 160 subjects would provide 80% power to detect a  $> 90\%$  probability of any benefit (HR  $> 1$ ) with high  $\Delta P$  at a type I error rate = 0.07 (10,000 simulations) assuming a minimally informative prior (centered at HR = 1 and precision = 10 [log scale]). In this phase 2A trial, we accept 80% power to detect a 90% probability of any benefit at a type I error rate  $< 0.1$  in anticipation of a larger trial.

## **6.5 Interim Analysis**

We have not planned interim efficacy analyses in this phase 2 trial. However, the DSMB will review the data and AEs no less frequently than every 6 months with a focus on safety. Early stopping will only be considered if SAEs or enrollment rates lead to concerns about continuation of the trial.

## 7 STUDY INTERVENTION

### 7.1 Description

PARMA is a randomized, open-label, two-arm, phase 2A clinical trial testing two different  $\Delta P$  (defined as peak pressure minus PEEP) strategies in pediatric ARDS. We will compare a high  $\Delta P$  (25 cmH2O) versus low  $\Delta P$  (15 cmH2O) strategy on time to hypoxemia resolution. The “device” being tested is ventilator settings on a CHOP standard Evita V500 (Dräger) ventilators.

We will also use Enlight 2100s (Timpel Medical) for this study. These are free-standing EITs with full graphical interface and ability to integrate with V500 ventilators, currently approved for both clinical and research use, with an existing EPIC order.

[figure not shown]
## 8 SAFETY MANAGEMENT

### 8.1 Clinical Adverse Events

Clinical adverse events (AEs) will be monitored throughout the study, daily during the intervention phase.

### 8.2 Adverse Event Reporting

The overall approach to categorizing and reporting AEs is provided below:

Unanticipated problems related to the research involving risks to subjects or others that occur during the course of this study (including SAEs) will be reported to the IRB in accordance with CHOP IRB SOP 408: Unanticipated Problems Involving Risks to Subjects. AEs that do not meet prompt reporting requirements will be summarized in narrative or other format and submitted to the IRB at the time of continuing review (if continuing reviews are required), or will be tracked and documented internally by the study team but not submitted to the IRB (if continuing reviews are not required).

### 8.3 Definition of an Adverse Event

An adverse event is any untoward medical occurrence in a subject who has received an intervention (drug, biologic, or other intervention). The occurrence does not necessarily have to have a causal relationship with the treatment. An AE can therefore be any unfavorable or unintended sign (including an abnormal laboratory finding, for example), symptom, or disease temporally associated with the use of a medicinal product, whether or not considered related to the medicinal product.

All AEs (including serious AEs) will be noted in the study records and on the case report form with a full description including the nature, date and time of onset, determination of non-serious versus serious, intensity (mild, moderate, severe), duration, causality, and outcome of the event.

## 8.4 Definition of a Serious Adverse Event (SAE)

An SAE is any adverse intervention experience occurring in relation to study procedures that results in any of the following outcomes:

- death,
- a life-threatening event (at risk of death at the time of the event),
- prolongation of existing hospitalization, or
- a persistent or significant disability/incapacity

Important medical events that may not result in death, be life-threatening, or require escalation of care may be considered a SAE when, based upon appropriate medical judgment, they may jeopardize the subject and may require medical or surgical intervention to prevent one of the outcomes listed in this definition.

A distinction should be drawn between serious and severe AEs. A severe AE is a major event of its type. A severe AE does not necessarily need to be considered serious. For example, nausea which persists for several hours may be considered severe nausea, but would not be an SAE. On the other hand, a stroke resulting in only limited disability may be considered a mild stroke, but would be an SAE.

### 8.4.1 Relationship of SAE to study procedures or other intervention

The relationship of each SAE to the study intervention should be characterized using one of the following terms in accordance with CHOP IRB Guidelines: definitely, probably, possibly, unlikely or unrelated.

## 8.5 IRB/IEC Notification of SAEs and Other Unanticipated Problems

The Investigator will promptly notify the IRB of all on-site unanticipated, SAEs that are related to the research activity. Other unanticipated problems related to the research involving risk to subjects or others will also be reported promptly. Written reports will be filed using the eIRB system and in accordance with the timeline below.

Type of Unanticipated Problem	Initial Notification (Phone, Email, Fax)	Written Report
Internal (on-site) SAEs Death or Life Threatening or Unexpected	24 hours	Within 3 calendar days
Internal (on-site) SAEs All other SAEs	7 days	Within 7 business days
Unanticipated Problems Related to Research	24 hours	Within 3 business days
All other AEs	N/A	Brief Summary may be at CR

### 8.5.1 Follow-up report

If an SAE has not resolved at the time of the initial report and new information arises that changes the investigator's assessment of the event, a follow-up report including all relevant new or reassessed information (e.g., concomitant medication, medical history) should be submitted to the IRB. The investigator is responsible for ensuring that all SAE are followed until either resolved or stable.

## 8.6 Investigator Reporting of a Serious Adverse Event to Sponsor

An independent Medical Monitor will be appointed by the PI. The CHOP-based PI ([name]) and/or research coordinators will report SAEs that are both unexpected and probably or possibly related within 24 hours of becoming aware of the event, with a detailed completed report sent to the IRB and Medical Monitor within three working days of the event. The Medical Monitor will assess all SAEs. For each SAE that is both unexpected and probably or possibly related to study, [name] will provide sufficient medical history and clinical details for a safety assessment to be made with regard to continuation of the trial. The Medical Monitor will sign each SAE report after review. All SAE reports will be retained, and all SAE reports will be available for review by DSMB members and NICHD staff.

Event	Expected in pediatric ARDS	Serious adverse event	Pre-specified safety outcome
Death	Yes	Yes	Yes
Pneumothorax requiring chest tube	Yes	Yes	Yes
Other air leak not requiring chest tubes	Yes	Yes	Yes
Ventilator-associated pneumonia	Yes	Yes	Yes
New or progressive multiple organ dysfunction syndrome (increase in organ failure score or death 7 days after randomization)	Yes	Yes	Yes
Cardiac arrest	No	Yes	No
Arrhythmia	No	Yes	No
Hypotension	Yes	No	No
Need for extracorporeal membrane oxygenation	Yes	Yes	No

Need for renal replacement therapy	Yes	Yes	No
Brain herniation	No	Yes	No
New-onset seizures (without history of epilepsy)	No	No	No
Pulmonary embolus/deep vein thrombosis	No	Yes	No
Placement of new tracheostomy	Yes	Yes	No
Increase in vasopressor support due to acidosis	Yes	No	Yes
Protocol termination due to failure criteria	No	No	Yes

In the unlikely event that the Medical Monitor believes an unexpected and study-related SAE warrants emergent cessation of enrollment in the trial, NICHD staff and the DSMB chairperson will be immediately consulted. If these individuals concur with the judgment of the Medical Monitor, or if the NICHD staff and the DSMB chairperson cannot be reached expeditiously, the Medical Monitor will notify the PI to pause enrollment in the trial. Resumption of enrollment will not occur without consent of the NICHD staff after discussion with the DSMB. In accordance with IRB requirements, the investigator will be required to report such events to the CHOP IRB. After notification of the NICHD Program Official or Project Officer, and the DSMB chairperson, of unexpected, study-related SAEs, decisions will be made whether to continue the study without change, and whether to convene the entire DSMB for an emergent meeting. If a decision is made to suspend enrollment in the trial, this will be reported to PI, who will be instructed to report this to the IRB. The DSMB will review all AEs (not necessarily serious, unexpected, and study-related) during scheduled DSMB meetings. The PI will prepare a Summary Report of AEs for the DSMB meetings, classified with the MedDRA coding system.

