As per NICHD practices, the DSMB recommendations will be signed and submitted to the NICHD officer (who is usually the Executive Secretary for the DSMB) within a reasonable time after the DSMB meeting. After approval or modification by the NICHD, the officer will forward the DSMB report to the PI. The PI will forward the report to the IRB. In the unlikely event that the DSMB recommends emergent cessation of enrollment in PARMA because of safety concerns, this communication will be made during the debriefing segment of the DSMB meeting. If the NICHD staff concur with this recommendation, the PI will notify all PARMA-related investigators and staff to cease enrollment immediately.

**Medical Monitor:** An independent Medical Monitor will be appointed. The CHOP-based PI ([name]) and/or study staff will report SAEs that are both unexpected and probably or possibly related to study procedures within 24 hours of becoming aware of the event, with a detailed completed report sent to the IRB within three working days of the event. The Medical Monitor will assess all SAEs. For each SAE that is both unexpected and probably or possibly related to study interventions, [name] will provide sufficient medical history and clinical details for a safety assessment to be made with regard to continuation of the trial. The Medical Monitor will sign each SAE report after review. All SAE reports will be retained, and all SAE reports will be available for review by DSMB members and NICHD staff.

In the unlikely event that the Medical Monitor believes an unexpected and study-related SAE warrants emergent cessation of enrollment in the trial, NICHD staff and the DSMB chairperson will be immediately consulted. If these individuals concur with the judgment of the Medical Monitor, or if the NICHD staff and the DSMB

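### The timed SAE report and its information package leave out definitely related events, and the SAE definition contains a relatedness condition that the rest of the protocol contradicts

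*Protocol*

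**What the plan says.** **Causality scale.** Section 8.4.1 has each SAE graded as "definitely, probably, possibly, unlikely or unrelated".

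**Expedited trigger.** In section 8.6 staff must "report SAEs that are both unexpected and probably or possibly related within 24 hours of becoming aware of the event", with a detailed report to the IRB and the Medical Monitor within three working days. The same section then sets a second duty, to supply enough history and clinical detail for a judgement on whether the trial should continue. It begins "For each SAE that is both unexpected and probably or possibly related to study". The Medical Monitor part of section 9.4.1 repeats both duties; its first reads "report SAEs that are both unexpected and probably or possibly related to study procedures within 24 hours of becoming aware of the event".

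**SAE definition.** Section 8.4 states: "An SAE is any adverse intervention experience occurring in relation to study procedures that results in any of the following outcomes". Death, a life-threatening event, prolonged hospitalization and lasting disability follow as the outcomes.

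**AE definition.** Section 8.3 takes the opposite line on causality for adverse events in general: "The occurrence does not necessarily have to have a causal relationship with the treatment".

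**Event table.** The table in section 8.6 classes named events as SAE or not by type. Death, ventilator-associated pneumonia and a new tracheostomy are among those marked as SAEs, with no condition about cause.

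**The concern.** There are two separate wording faults.

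First, a rule meant to speed up the most worrying reports names two grades of relatedness and omits the strongest. Taken literally, an unexpected SAE judged possibly caused by the study has a deadline and a required information package under 8.6 and 9.4.1, while one judged definitely caused by it has neither under those sections.

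Second, if relation to study procedures is part of the definition, someone must judge cause before an event can be called an SAE. Clinicians and investigators are not blinded (sections 3.2 and 9.1.2), and section 9.4.2 accepts that pneumothorax and other air leak could plausibly be more frequent with the high ΔP strategy. A causality judgement made with knowledge of the arm could then affect which events are called SAEs in each arm.

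The label carries weight here. Section 4.4 gives no explicit stopping rules, section 6.5 considers early stopping only if SAEs or enrollment rates cause concern, and section 6.3.3 singles out SAEs for detailed description.

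**Working it through.** No arithmetic beyond counting applies, and the plan states no figure to reproduce. The check sets the provisions side by side.

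**1. The trigger against the scale**

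- The scale in 8.4.1 has 5 grades. Three express relatedness (*definitely*, *probably*, *possibly*) and two do not (*unlikely*, *unrelated*).
- The trigger appears 2 times in 8.6 (timed report; information for the continuation judgement) and 2 times in 9.4.1, so 2 + 2 = 4 statements.
- Each statement names 2 of the 3 related grades, and the missing grade is always the strongest.
- Later text in 8.6 and 9.4.1, on halting enrollment, speaks simply of study-related SAEs. The wording therefore varies even within these sections.

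**2. Do other provisions cover the missing grade?**

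| Provision | Covers a definitely related, unexpected SAE? | What it leaves open |
|---|---|---|
| 8.5, IRB notification | Yes; no grade is excluded, and the table has a 24-hour row for fatal, life-threatening or unexpected SAEs | Does not mention the Medical Monitor |
| 8.7, unanticipated problems | Probably; IRB and NICHD within 24 hours | Also requires that the event suggest greater risk than previously known; sets no reporting route to the Monitor |
| 8.6 and 9.4.1, Monitor's scope | Yes; the Monitor assesses all SAEs and signs each report | Gives no deadline and no required content |

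The event would therefore be assessed by the Monitor and would probably reach the IRB. What is missing on the literal text is the timed report under 8.6 and 9.4.1 and the duty to supply detail for the continuation judgement.

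**3. The SAE definition against the rest of the safety section**

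- Against 8.3: an AE needs no causal link, and seriousness and causality are recorded as separate items for every AE. Under 8.4, seriousness depends partly on relatedness.
- Against 8.4.1: an SAE may be graded *unlikely* or *unrelated*. If relation to procedures were required, those 2 of the 5 grades could hardly apply.
- Against the 8.6 table: 12 of its 16 events are marked as SAEs and 4 are not (12 + 4 = 16). None of the 12 carries a relatedness condition.

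The definition thus stands alone against three other provisions.

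**4. Could the phrase in 8.4 mean timing only?**

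The heading of 8.4.1 uses relationship to study procedures for causality, and 9.4.1 uses related to study procedures in the same sense. Where 8.3 means timing, it says so expressly. The causal reading is the more natural one, though not the only one.

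**The case against.** The strongest reply is that this is loose drafting with little practical effect, and much of that stands.

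- A reader might infer that a definitely related unexpected SAE falls outside the Medical Monitor's review. The protocol does not support that: 8.6 and 9.4.1 both say the Monitor assesses all SAEs and signs each report. Moreover, the 24-hour clause names no recipient in either section, and 9.4.1 sends the detailed report only to the IRB. A separate 24-hour route to the Monitor is therefore not clearly established for any grade.
- A reader might also infer that events judged unrelated can never be SAEs. That follows only from the literal 8.4 definition; the 8.4.1 grades and the 8.6 table point the other way.
- Filtering of safety data by arm is largely blocked. All AEs go on the case report form whatever their cause (8.3). The DSMB reviews all AEs, not only serious or related ones (8.6 and 9.4.1). Mortality, pneumothorax requiring chest tube, other air leak, ventilator-associated pneumonia and organ dysfunction are outcomes in their own right (5.3 and 6.2), with no relatedness condition.
- It is hard to imagine an investigator reporting a possibly related event and holding back a definite one. The trigger was probably meant as a minimum threshold.

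These points limit the consequence. They do not make the text right: the operative trigger still omits a grade that the protocol itself defines, and the definition still contradicts three other provisions.

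**Conclusion.** The point holds as a defect in safety-reporting wording, with two limited parts.

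1. The timed 24-hour and three-working-day report, and the required detail for the continuation judgement, do not on their wording extend to definitely related SAEs. The gap goes no further than that.
2. The relatedness condition in 8.4 conflicts with 8.3, 8.4.1 and the 8.6 table. Read literally, an unblinded causality judgement could affect which events are described as SAEs under 6.3.3 and weighed as SAEs when early stopping is considered under 6.5. It would not remove events from the AE record, from DSMB review or from the separate harm endpoints.

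The first part rests on the literal wording and is probably a drafting slip. The second assumes the causal reading of the phrase in 8.4. The documents do not allow an estimate of how many events either part would touch. No efficacy, alpha, power or sample-size figure is affected. Correction is still worthwhile because SAEs are one of only two stated grounds for early stopping in an unblinded trial without explicit stopping rules.

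**What to change.** Reconcile sections 8.3, 8.4, 8.4.1, 8.6 and 9.4.1:

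- In 8.6 and 9.4.1, word all four statements of the trigger as *definitely, probably or possibly related*.
- In 8.4, remove the condition about relation to study procedures, so that seriousness is judged by outcome (keeping the existing clause on important medical events) and relatedness is recorded separately under 8.4.1.

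The cost is a wording amendment. Design, endpoints, treatment rules, sample size and the planned analyses stay as they are.
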